SUI Stress Urinary Incontinence

SUSAR Suspected Unexpected Serious Adverse Reaction

TCA Tricyclic antidepressants

TVT Tension free Vaginal Tape

UOP Urethral Opening Pressure

UP Urethral Pressure Profilometry

UPR Urethral Pressure Reflectometry

Summary

Stress urinary incontinence (SUI) and fecal incontinence are common disorders of the general population. Pharmacological treatment can increase sphincter tone for the external urethral sphincter and thus better the symptoms of SUI or increase the tone of the external anal sphincter and thus better symptoms of fecal incontinence. In Denmark, only one registered medicine exists for the treatment of SUI; duloxetine. There is no approved drug for the treatment of fecal incontinence, which acts on the tone of the internal or external anal sphincter. We want to investigate an alternative medical treatment in the form of imipramine; a tricyclic antidepressant (TCA) with known adverse reactions. Previous studies with imipramine have shown varying degrees of efficacy in patients with SUI. Imipramine has never been studied in relation to fecal incontinence. Reflectometry is a simple, safe and valid way to assess the pressure conditions in the urethra (UPR) and the anal canal (AAR). In total, we will examine 16 healthy female subjects in a double-blind, placebo-controlled, crossover study, in which single-dose imipramine 50 mg or placebo is given. The effect on SUI is assessed by the change in Urethral Opening Pressure (UOP) measured by Urethral Pressure Reflectometry (UPR). UOP has previously been shown to be a good objective measure, which correlates with the subjective effects of drugs on SUI. UPR requires fewer subjects compared to urinary diaries or Urethral Pressure Profilometry (UPP) to find statistically significant differences (greater power). In case of change in UOP of more than 10 cm H₂O compared to placebo, the effect is clinically relevant and there will be a basis for further studies in relation to reduction in urine incontinence episodes, side effects and subjective improvement with imipramine use in patients with SUI. This may, in the long term, it may allow medical treatment with imipramine in patients with SUI who do not tolerate duloxetine. The Anal Acoustic Reflectometry (AAR) measurements are exploratory. We will examine the pressure conditions in the anal canal after intake of imipramine 50 mg to assess whether imipramine could have a role in the treatment of stool incontinence, and examine the statistical variation of AAR, so that it will be possible to estimate the required number of subjects in phase 1 studies in which AAR can be used to assess the effect of new drugs against fecal incontinence.

Background

Stress urinary incontinence (SUI):

SUI is frequent with a prevalence of 30 % to 50% with the highest prevalence from 25 to 49 years of age (1). SUI is defined symptomatically as involuntary urine leakage during increased abdominal pressure, e.g. by coughing, sneezing, lifting or other physical activity (2). First-line treatment of SUI is conservative in terms of weight loss, smoking cessation, pelvic floor training and intravaginal devices (pessaries, tampons, etc.). In case of failure of conservative treatment, surgical treatment is offered, and the evidence is solid for mid urethral, suprapubic loosely fixed polypropylene slings (TVT, etc.), which can be performed as outpatient interventions in local analgesia (3).

Medical treatment of SUI:

Drug therapy in patients with pure SUI is generally used only, when surgery is contraindicated, or not desired by the patient (3). In Denmark, only one drug, duloxetine, is registered with the indication "stress urinary incontinence in women". However, the effect is small and, compared to placebo, only a few percent of patients have effect on SUI symptoms (11% versus 8%). Also, the number of incontinence episodes is reduced by only approx. 1 pr. day (4). Side effects are frequent, especially side effects from the central nervous system (CNS) such as nausea, sleep disorders, nervousness, headache, decreased libido and anorgasm (4). Treatment effects and side effects can be assessed within a few weeks and, in the absence of efficacy, treatment should be stopped (4).

Fecal Incontinence:

Fecal incontinence occurs in up to 8% of the general population (5-7). Fecal incontinence is often due to decreased function of the internal or external sphincter either due to trauma or degeneration (8).

Medical treatment of fecal incontinence:

A possible treatment may be to increase the pressure in the anal canal pharmacologically (9). Thus, it has been shown that resting pressure measured by anal manometry is increased by local treatment with methoxamine (potent adrenergic alpha agonist) (10). Unfortunately, a clinical effect on anal incontinence in this topical treatment in a clinical placebo controlled trial (11) has not been demonstrated.

Imipramine in general and side effects:

We want to investigate an alternative medical treatment in the form of the TCA imipramine. Imipramine is approved for the treatment of moderate to severe depression and for enuresis nocturna (urination during sleep) (12). Imipramine is an old preparation and has been on the market in Denmark since 1976 (13). The side effects are known, and the most frequently observed are dry mouth, dizziness, sexual disorders, withdrawal symptoms by abrupt discontinuation, myoclonus, confusion and blurred vision (13).

Imipramine - pharmacodynamics:

Imipramine affects the catecholamine metabolism in the CNS. Imipramine is a potent inhibitor of noradrenaline and serotonin (5 - HT) reuptake by the presynaptic, noradrenergic nerve endings. Imipramine is one of the least sedative TCAs and has only moderate antimuscarinic activity (13).

Imipramine - pharmacokinetics:

Imipramine is rapidly and completely absorbed from the gastrointestinal tract after oral administration, and the plasma concentration peak within 1 hour. Imipramine undergoes first pass metabolism in the liver to the primary, active metabolite, desimipramine via the enzyme CYP2C19. Imipramine is eliminated mainly in the urine and the half-life is 6 to 18 hours - that is to say all imipramine is eliminated after

approx. 4 days if liver and kidney function is normal.

Imipramine and SUI:

Imipramine has previously been used for the treatment of SUI. There is, however, no randomized studies that illustrate the efficacy and side effects (3), but two smaller studies have described a positive effect on the number of urinary incontinence episodes, and the pressure profile in the urethra measured by UPP (14,15). The mode of action of treating SUI is unknown (3). Rat studies have shown that immediately following imipramine administration the threshold for the vesicourethral micturition reflex on CNS level is increased, whereby emptying of the bladder is inhibited. Similarly, cat studies have shown that stimulation of 5-HT receptors modifies spinal reflexes, which are involved in bladder control. Onuf's nucleus (ON), located at the sacral part of the medulla spinalis, contains the motor neurons that control the activity of the external urethral sphincter. ON is affected by both serotonergic and noradrenergic nerve cells. Thus, it is pharmacodynamically plausible that an increased concentration of norepinephrine and serotonin in the synaptic cleft by imipramine administration may affect the bladder and the external urethral sphincter, so that the bladder emptying is inhibited (16).

Imipramine and Stool Incontinence:

The striated external sphincter of the anal canal, like the urethral sphincter, is innervated by ON (17). Theoretically, TCAs could increase the maximum squeeze pressure and, to a lesser degree, the resting pressure. In an older, uncontrolled study, amitriptyline (another TCA) had clinical effect on stool incontinence (18). In this study, in addition to reduced intestinal peristalsis, increased resting and squeezing pressure in the anal canal was also measured. The squeeze pressure increased from 108 cm H₂O to 123 cm H₂O, which, however, was statistically insignificant. A pressure increase of 15 cmH₂O or more is probably clinically relevant. It has been shown that opening pressures at rest and during squeeze measured with AAR correlate with severity of stool incontinence, while the same does not apply to rest and squeeze pressure measured by conventional manometry (19). It is therefore possible, that AAR can provide a more reliable assessment of new pharmaceuticals for the treatment of fecal incontinence. Variation between the predose measurements and the changes in the placebo period can clarify whether AAR is suitable for phase 1 studies, and can be as a basis for sample size calculations for future studies.

Imipramine dose and time for UPR and AAR:

Imipramine will be administered as a single 50 mg dose, which is the recommended starting dose for treatment with imipramine (12). UPR will be performed 1 hour after tablet intake, corresponding to the time for peak plasma concentration, t_{max} (13). AAR will be performed immediately after UPR.

Objective

We will examine, whether imipramine increases the resistance of the external, urethral sphincter, and hence whether imipramine could have a role in the medical treatment of SUI, where there currently exists only on medication on the Danish market with this indication.

Exploratory, we will investigate if imipramine increases the resistance of the anal canal, and thus if imipramine could have a role in the medical treatment of fecal incontinence. We will investigate the variation in the measurements of AAR, and thus whether AAR can be used for future phase 1 studies with pharmacological treatment of fecal incontinence and allow sample size calculations for such studies.

Hypothesis

The 0-hypothesis is that there is no difference in UOP in healthy subjects before and after single-dose placebo and single-dose imipramine 50 mg. The alternative hypothesis is that imipramine single dose increases UOP with a minimum of 10 cm H₂O over placebo.

Explorative hypotheses for AAR measurements:

- 1) Anal Acoustic Reflectometry can be used to test pharmaceuticals with effect on the internal and external anal sphincter.
- 2) Imipramine has an effect on the anal opening pressure during squeeze.

Purpose

The aim is investigate whether imipramine has a role in the medical treatment of SUI and / or faecal incontinence and to assess whether AAR in the future can be used for phase 1 trials for pharmaceuticals against fecal incontinence.

Design

The study is a placebo-controlled, double-blind, randomized, crossover study. We recruit 16 healthy female subjects and investigate them on two different trial days preceded by a screening day.

The participants are recruited and called for an information day, where written and oral information is given. Subsequently, there is the possibility of reflection time (up to 7 days) before signing written consent. When the written consent is signed, the participants are summoned for the screening day, when the inclusion criteria and the exclusion criteria are reviewed incl. objective examination by doctor and measurement of resting blood pressure. If inclusion criteria are fulfilled and none of the exclusion criteria are met included the participant and assigned a blinded medication kit. On the same day (if consent is given immediately) or the second day (if time is needed before signing the consent), trial day 1 is performed; see under procedures. There is a wash out period of minimum 7 days between trial day 1 and trial day 2. Five days after trial day 2, the participants are called by to identify and follow-up any Adverse Events (AE).

Production of placebo, packaging, blinding, randomization and labeling is handled by Region Hovedstadens Apotek according to GMP. Region Hovedstadens Apotek produces 16 medicine kits consisting of placebo and imipramine. Medicine kits are randomized by Region Hovedstadens Apotek. Each medicine kit is assigned one randomization number from 1 to 16. Of these 16 medicine kits, 8 will contain placebo on trial day 1 and imipramine on trial day 2, and 8 medicine kits will contain imipramine on trial day 1 and placebo on trial day 2. The contents of the medicine kits are blinded to everyone involved until data collection is completed (unless individual subjects are unblinded based on side effects). When trial participants are included they are assigned a randomization number: First test participant gets number 1, next participant gets number 2 etc. This corresponds to the a randomization number on the medicine kit from which the patient receives trial medication. In addition, 4 extra medicine kits are produced which can be used in the event of a dropout.

Inclusion criteria

- Signed informed consent.
- Healthy.
- Woman.
- Non-smoking.

- Age 18 years to 55 years, both inclusive.
- Normal weight, ie. BMI 18.5 to 30.0 kg / m². Weight minimum 50 kg.
- Consent not to breastfeed during the study or 1 week after the study.
- Negative pregnancy test on trial day 1 and trial day 2.
- Consent not to get pregnant during the study.
- Consent not to participate in other clinical trials concurrently with this study.

Inclusion criteria

- Known hypersensitivity to imipramine.
- history of significant cardiovascular, gastrointestinal, endocrinologic, haematologic, immunological, metabolic or genitourological disease (incl. surgery after pelvic trauma, urethral hypermobility or prolapse of the organs of the pelvis), pulmonary disease, neurological disease, dermatological disease, psychiatric disease, kidney disease, malignant disease and / or other major diseases assessed by the investigator.
- History of or symptoms of urinary incontinence.
- Treatment of infection at least one week before trial day 1, ie. fever or symptoms of viral infection, bacterial infection (including upper respiratory tract infection) or fungal infection (not cutaneous).
- Clinically significant findings assessed on clinical study on screening day.
- Pregnant.
- Pulse <40 or > 100 beats per minute. Mean systolic blood pressure > 140 mmHg or mean diastolic blood pressure > 90 mmHg (average of 3 measurements on screening day). If blood pressure or heart rate differs from this, an additional 3 measurements can be performed.
- Prescription drugs or over-the-counter or natural remedies at least 2 weeks before trial day 1 and trial day 2. Exclusive paracetamol up to 2 g / day and exclusive contraception.
- Smoking 3 months before trial day 1 and trial day 2.
- Alcohol consumption, ie. > 14 drinks per week within 3 months before the trial day 1 and experimental day 2.
- Substance abuse within 3 months before trial day 1 and trial day 2.
- Any condition that allows the investigator not to include the subject.

Recruitment

Healthy volunteers from previous UPR trials in Zelo Phase-1 unit, which have expressed interest in participating in future UPR studies will be informed about the trial and have the opportunity to contact us for inclusion. If there are not recruited enough subjects this way, we will recruit with advertisement on www.forsøgsperson.dk. All recruitment - and the information - must be approved by the Regional Research Ethics Committee.

Reimbursement

Allowance of DKK 125 per hour and DKK 1000 in nuisance bonus for the UPR measurements and AAR measurements on trial day 1 and trial day 2. Thus, compensation of DKK 250 is granted for information day and screening day (approximately 2 hours), DKK 1375 for trial day 1 (3 hours and 1000 DKK nuisance bonus) and 1375 DKK for trial day 2 (3 hours and 1000 DKK nuisance bonus). A total of DKK 3000 in allowance if the entire trial is carried out. The reimbursement must also be authorized by the Regional Research Ethics Committee.

Procedures

Information day: Subjects receive written and oral information about the trial. The subject is entitled to an assessor. Total approx. 30 minutes duration. The subject is offered reflection time, but if the subject is ready to sign written consent, the next part is done immediately.

Screening day: Written consent is obtained. An objective examination is carried out and the medical history and information about the consumption of medicine incl. herbal remedies and supplements are obtained. Objective examination by doctor. Blood pressure x3 is measured after 5 minutes of rest in a supine position. Total approx. 1 hour duration.

Trial day 1: Pregnancy is excluded by pregnancy test via urine sample. The subject is randomized to one of the 16 prefabricated, blinded medicine kits. The subject's bladder is emptied by sterile disposable catheterization and then 150 ml of 9% NaCl are instilled the bladder. UPR is performed with 10 measurements, while the subject is relaxing the pelvic floor. Then 5 measurements while the subject is squeezing the pelvic floor. Measurements in the urethra are followed by measurements in the anal canal, where also 10 measurements are made while the subject is relaxed, and 5 measurements while the subject squeeze in the pelvic floor. The subject consumes two tablets according to the randomization and trial day. This will be either two placebo tablets or two tablets of Imipramin DAK 25 mg. The subject relaxes for 1 hour. Again, the bladder is emptied by sterile disposable catheterization and then the bladder is filled with 150 ml of 9% NaCl followed by UPR with 10 measurements, while the subject relaxes the pelvic floor, then 5 measurements while the subject squeezes the pelvic floor. The measurements in the urethra are followed by measurements in the anal canal, where also 10 measurements are made while the subject is relaxed, and 5 measurements while the subject is squeezing the pelvic floor. After that, any AE and ADR are registered. Total approx. 3 hours duration.

Trial day 2 : Minimum 1 week after trial day 1 to ensure elimination of the drug. Procedure is identical to trial day 1. Total approx. 3 hours duration.

A total of 4 days of total approx. 8 hours duration.

Methods

UPR

UPR is a validated method for simultaneously measuring the pressure ratio and the cross-sectional area of the urethra. A very thin and very flexible polyurethane bag is introduced into the urethra. Sound waves measure the cross-sectional area of the urethra while pumping air into the polyurethane bag, thereby providing knowledge of the pressure in the urethra. The opening and closing pressure, opening and closing elasticity and the hysteresis can thus be measured by UPR. UPR is more reproducible, with lower variability (and therefore greater statistical power), compared to UPP (20,21). No risk or complication of the procedure has been demonstrated beyond limited discomfort by catheter insertion and a minor risk of cystitis, which, however, is minimized by sterile technique.

AAR

Anal Acoustic Reflectometry (AAR) is a reproducible method of simultaneously measuring pressure and cross-sectional area in the anal canal (22). It has been shown that opening pressure at rest and during squeeze measured with AAR correlates with severity of fecal incontinence, while the same does not apply to rest and squeeze pressure measured by conventional manometry (19). AAR are performed with the same equipment and catheters as used in UPR. No risk or complications of the study have been demonstrated beyond limited discomfort by having catheters inserted into the anal canal.

Statistics

Power calculation:

The primary endpoint is the difference (*delta*) in average baseline UOP and 1-hour UOP. A clinically relevant *delta* between placebo and imipramine is estimated to be 10 cm H₂O. From previous UPR studies of pharmacological intervention vs. placebo there was a residual mean squared error (RMSE) of 5.4 for measurement of UOP (20) - this corresponds to the standard deviation (SD) of the difference in UOP measurements. This gives Cohen's *d* of $10/5.4 \approx 1.85$. We will investigate 16 subjects to minimize the risk of type II errors. For un-paired t-test, Cohen's *d* = 1.85, $\alpha = 0.05$ and $n = 16$, we have strength = 99% to detect a clinically relevant difference of 10 cm H₂O (23).

Power calculation for AAR:

For a sample size of 16 subjects. A clinically relevant difference of 15 cm H₂O in pinch opening pressure, SD of 21 for squeeze opening pressure (22), alpha of 0.05, gives a power of 80%.

Results presentation

Baseline characteristics (age and weight) of trial participants are summarized with mean and SD. The results from UPR and AAR are described descriptively with mean and SD. Specifically, within-subject SD for AAR is also described to allow future sample size calculations. The UOP and opening pressure of the anal sphincter for placebo / imipramine are analyzed according to Grizzle's method for cross-over studies (24), that is with a CROS test: One unpaired, two-sided t-test to assess the effect of the intervention. A p value < 0.05 is deemed statistically significant and an average difference greater than 10 cm H₂O for UPR and 15 cm H₂O for AAR are deemed clinically significantly.

Time schedule

Enrollment begins when the necessary permits are available and continue with inclusion until 16 subjects are examined according to this Protocol.

Expected first trial day for first subject: Earliest 18/4 2017.

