The first meeting is an information interview with one of the doctors responsible for the trial. Here, the subject will be informed orally and given written information. The person in question has the right to bring along an assistant. The meeting will take place in quiet undisturbed locations with time for questions. The information itself deals with the experiment and its advantages and disadvantages and must be easily understood by the subject.

The subject is informed about the right to refuse information about significant health conditions. The informing doctor is responsible for ensuring that the information is understood. The subject then has the right to a minimum of one-week reflection time.

On the screening day, written consent is obtained from the subject. At the declaration of consent, the investigator of the trial notes that written and oral information is given as stated above.

The subjects are informed that they may withdraw their commitment to participate in the trial at any time without this having any effect on current or subsequent treatment or controls.

The subject is informed if, in the course of the experiment, significant information about his or her health condition arises he/she will be informed of this, unless the subject explicitly states that he does not want this information.

Results

When the results of the study are available, one of the project's doctors will if possible inform the participating subjects about the result. Information on the participating subjects are protected under the *Act on processing of personal data* and the *Law on patients' rights* .

Side effects and risks

Sterile disposable catheterization and UPR and AAR measurement results in immediate discrete discomfort during measurement and minimal risk of developing cystitis, which is minimized by sterile technique.

The side effects of imipramine are well known (12) . The known side effects of imipramine are available in the Summary of Product Characteristics 4.8.

The psychiatric and cardiac side effects are considered irrelevant in relation to a single dose. Possible adverse reactions are expected to primarily be anticholinergic (e.g. dry mouth, dizziness, and hypotension) and hypersensitivity reactions such as rash and urticaria.

Pregnancy

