Imipramine does not appear to be associated with an increased risk of malformations (25–27). There is a risk of withdrawal symptoms associated with delivery. The subjects are screened for pregnancy with pregnancy test (urine) prior to both test days. Only single-dose low dose (50 mg) imipramine is given. It is therefore assessed that there is no risk if pregnancy occurs immediately after the trial day, since the concentration of the drug is reduced to approx. 6- 40% (half-life 6-18 hours) of the dose and because maximum dose is already low, and as the substance has not been shown to be teratogenic in spite of the high usage for many years.

Pros and cons

Disadvantages: Possible side effects of the study drug (though low dose and single dose), low risk of cystitis associated with UPR (minimized by sterile technique), and discomfort associated with UPR and AAR (transient nuisance) .

Advantages: The subjects will have no immediate advantage by participating in this trial. The participants contribute to the gathering of useful new knowledge about the effect of the trial drug on the pressure in the urethra and the anal canal. This can be beneficial for future patients with stress urinary incontinence and fecal incontinence.

Adverse Events

All Adverse Events are registered on the CRF at the following times:

- At the end of trial day 1 and trial day 2.
- At the start of the trial day 2 (AEs since trial day 1).
- Five days (corresponding to > 5 half-lives) after the last test day (contact by phone).

Any SAE (Serious Adverse Events), is immediately (within 24 hours) reported to the sponsor ([name]) according to the SOP for this. All AEs are followed until they are completed - also beyond the duration of the trial. AE is terminated when the subject is in normal health or stable condition. All AE, Adverse Drug Reactions (ADR), Serious Adverse Reactions (SAR), Serious Adverse Events (SAE) and Suspected Unexpected Serious Adverse Reactions (SUSAR) are handled in accordance with ICH-GCP and applicable legislation (from the Danish Medicines Agency):

"The sponsor must immediately notify the Danish Medicines Agency if, during the trial, unexpected and serious suspected adverse reactions (Suspected Unexpected Serious Adverse Reactions , SUSARs) are observed, cf. 2. No. 1.

The definitions are as follows, cf. the Executive Order on clinical trials:

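### The bladder-fill instruction specifies 9% NaCl at both fills, ten times isotonic strength and most likely a slip for 0.9%

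*Combined protocol and SAP*

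**What the plan says.** The instruction is in the Procedures section of the combined protocol and SAP, under Trial day 1. Before dosing, the bladder is emptied by catheter and "then 150 ml of 9% NaCl are instilled the bladder". One hour after the tablets, the bladder is emptied again and "then the bladder is filled with 150 ml of 9% NaCl followed by UPR with 10 measurements". For Trial day 2 the text says only "Procedure is identical to trial day 1".

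Three other places describe the risk of the procedure:

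- Methods, UPR: "No risk or complication of the procedure has been demonstrated beyond limited discomfort by catheter insertion and a minor risk of cystitis".
- Side effects and risks: catheterisation and the measurements together bring what "results in immediate discrete discomfort during measurement and minimal risk of developing cystitis".
- Pros and cons: again a low risk of cystitis and transient discomfort, and nothing about the fill solution.

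The available text gives no other NaCl concentration, no product name and no reason for using a hypertonic solution.

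**The concern.** Sodium chloride at 9% (w/v) is ten times the strength of isotonic 0.9% saline. A deliberate choice of such a fluid would need a rationale and a risk statement, and the protocol has neither. Either the figure is wrong, or the risk text is incomplete. The first is much the likelier, because discomfort and a small risk of cystitis are what one would list for a routine saline fill.

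What is at stake is the safety of healthy women who stand to gain nothing personally from taking part. The figure is in the step that staff are meant to follow, not in background text. As written, no emptying is specified between the pre-dose fill and the catheterisation one hour after dosing. Unless the subject voids, the first fill therefore stays in the bladder for at least that hour. There is also a compliance side: a site that sensibly uses 0.9% would be departing from the letter of its own protocol.

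**Working it through.** The plan states no derived figure to reproduce. The check is a search of the text followed by unit arithmetic.

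**Inputs from the protocol**

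- Volume per fill: 150 ml (Procedures, Trial day 1, both fills).
- Concentration as printed: 9%, at both fills. These are the only two mentions of NaCl in the available text.
- Fills per trial day: 2 (before dosing and one hour after).
- Trial days: 2, with the same procedure on each.
- Completers: 16 (Drop out section).

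**Inputs from outside the protocol**

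- Percent is read as grams per 100 ml.
- Molar mass of NaCl is 58.44 g/mol.
- Full dissociation into two ions is assumed, so the osmolarities are ideal values.

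**Number of fills governed by the instruction**

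- Per completer: 2 × 2 = 4.
- Across completers: 4 × 16 = 64.

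**Formulas**

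- Mass per fill = concentration (mg/ml) × 150 ml.
- Molarity = (g/L) / 58.44.
- Osmolarity = 2 × molarity.

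| Quantity | As printed, 9% (90 mg/ml) | At 0.9% (9 mg/ml) |
|---|---|---|
| NaCl per fill | 90 × 150 = 13,500 mg = 13.5 g | 9 × 150 = 1,350 mg = 1.35 g |
| NaCl per trial day (2 fills) | 27 g | 2.7 g |
| NaCl over four fills | 54 g | 5.4 g |
| Molarity | 90 / 58.44 = 1.540 mol/L | 9 / 58.44 = 0.154 mol/L |
| Osmolarity (ideal) | about 3,080 mOsm/L | about 308 mOsm/L |

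The ratio is 10 in every row. That is the gap produced by writing 9% where 9 mg/ml is meant.

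The masses are amounts instilled under a literal reading. They are not amounts absorbed. The four-fill total is not a simultaneous exposure, because the bladder is emptied before each fill and the trial days are at least 7 days apart.

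**Effect on the trial's inference.** The same fill is specified before and after dosing, in both periods and for both treatments. A wrong concentration used throughout would not by itself bias the comparison of imipramine with placebo. No power or sample-size figure in the Statistics section depends on it.

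**The case against.** The strongest counter-argument is that the fault may lie in the reading of the PDF. A per-mille sign read as a percent sign would turn 9‰ (that is, 0.9%) into 9% at both places and leave decimals elsewhere intact. This cannot be excluded without the source file, so the source should be checked. It remains a conjecture: no per-mille sign appears anywhere in the available text. A simply dropped decimal is unlikely, since the same figure appears twice and other decimals survive (0.05, 5.4 and 1.85 under Statistics; 18.5 in the inclusion criteria).

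A second argument is that this is one editorial slip among several in the document and that trained staff would not act on it. The Recruitment section refers to "Healthy volunteers from previous UPR trials in Zelo Phase-1 unit", so the unit has done this before, and the Administrative conditions section calls for ICH-GCP conduct, monitoring and regulatory and ethics approval. These safeguards are real and make literal use unlikely. None of them states the concentration, however, and the protocol is the document against which conduct is monitored. Other slips are awkward wording; this one is a tenfold wrong quantity in an invasive step.

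A third argument is that gram totals make a suspected misprint look like a measured hazard. It is fair that the tenfold ratio and the strength of the solution are what matter, and that the cumulative total should carry no weight as an exposure.

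Finally, the risk text already fits a 0.9% fill, so there is arguably no safety gap beyond the misprint. That is true if 0.9% was intended, but it is a reason to correct the misprint, not to leave it.

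**Conclusion.** The instruction is wrong as written and should be corrected. It calls for a fill of about 3,080 mOsm/L where an isotonic one would be about 308 mOsm/L, at every one of four fills per completer. Nothing in the available text justifies or corrects the figure.

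Two assumptions carry this conclusion: that the source file prints 9% as the extracted text does, and that 0.9% was meant. The second is an inference from the missing rationale, the risk statements and the exact factor of ten; the protocol does not say so.

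The point is one of safety and of the accuracy of a working instruction. It has no bearing on the primary endpoint, power, sample size or analysis. No claim is made about what the site would actually do, or about the subject information, which was not available.

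**What to change.** Check the source file. If it prints 9%, change both occurrences under Procedures, Trial day 1, to 0.9% NaCl (9 mg/ml). Trial day 2 inherits the correction. Make the same change in any site worksheet that repeats the figure, and have the investigator confirm the product before the first subject.

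Only if a 9% solution is truly intended should the figure stay. In that case the protocol must give the reason and describe the risk in Methods (UPR), Side effects and risks, and Pros and cons.

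The cost is two wording corrections and any matching worksheet edit. Subjects, visits, sample size and analysis do not change.
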